All enrolled patients will undergo a leukapheresis after resection for harvest of PBLs for generation of DCs. Patients will then receive approximately 6 weeks of standard of care RT and concurrent TMZ at a standard targeted dose of 75 mg/m²/d (please see Package Insert uploaded in eIRB for standard therapy). Patients should start RT within approximately 6 weeks of surgery. Patients who either experience progressive disease during radiation, are dependent on steroid supplements above physiologic levels at time of first vaccination, are unable to tolerate TMZ, or whose DCs or PBLs fail to meet release criteria will be withdrawn from the study and replaced and will not undergo repeat leukapheresis. For patients whose initial leukapheresis yields less than 3 vaccines, repeat leukapheresis may be obtained a minimum of 2 weeks from the previous leukapheresis (and may be repeated as needed) if pre-pheresis blood work is within the Apheresis Center's parameters and as long as this does not cause a significant delay in treatment for the patient. At the post-RT clinic visit where patient's MRI and blood work is evaluated prior to ordering the first post-RT cycle of TMZ, patients will be randomized to receive DC vaccination with one of three treating regimens: Group I: unpulsed DC pre-conditioning prior to vaccination #4; Group II: Td pre-conditioning prior to vaccination #4; or Group III: basiliximab infusions at vaccination #1 and #2 with Td pre-conditioning prior to vaccination #4. As of March 2017 (AMD 49), randomization of patients to Group III has been terminated. Please see Section 9.1.1 for a detailed outline of the randomization strategy for vaccine site pre-conditioning and Section 9.1.7 for a detailed description of the double blinding process. The study cycle of TMZ comprises a targeted dose of 150-200mg/m²/d for 5 days every 5 (± 1) weeks. All patients will receive up to a total of 10 DC vaccines given bilaterally at the groin site unless progression occurs. DC vaccines will be given i.d. and divided equally to both inguinal regions. DC vaccines #1-3 will be given every two weeks, thus delaying the initiation of TMZ cycle 2 for all patients. All remaining TMZ cycles will continue every 5 (± 1) weeks. Before the first DC vaccination, patients will receive 0.5 mL of Td (tetanus and diphtheria toxoids adsorbed) intramuscularly into the deltoid muscle to ensure adequate immunity to the tetanus antigen. The Td vaccine will be obtained through Duke Investigational Chemotherapy Services (ICS) Pharmacy. All patients will undergo leukapheresis again for immunologic monitoring with specific assessment of baseline antigen-specific cellular and humoral immune responses and further DC generations 4 ± 2 weeks after vaccine #3.

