Effective March 2017 (AMD 49), randomization of patients to Group III has been terminated due to results from the related REGULATE study (IRB # Pro00000581), a study that evaluated the safety, toxicity, and efficacy of T Reg inhibition with basiliximab. REGULATE was used as the model for Group III in ELEVATE. Recent analyses of REGULATE data have shown that although the regulatory T cells were depleted, the cells did not show pp65 reactivity and their activation status was reduced. Patients previously randomized to Group III will continue on study as planned.

With AMD49, approximately 79 patients will ultimately be randomized to subsequent treatment after completion of radiation treatment with concurrent temozolomide, including 9 patients previously randomized to Group III. As originally planned, an interim analysis will be conducted after approximately 35 patients have been randomized to Groups I and II each in order to make a decision concerning the accrual of additional patients to address efficacy objectives within patient subgroups defined by CMV status (see Section 15.8).

All Groups

All patients will then be vaccinated in conjunction with subsequent TMZ cycles every 5 ± 1 weeks for a total of 6 to 12 cycles after RT at the discretion of the treating oncologist. DCs will be given on day 21 ± 2 days of each TMZ cycle. DC vaccinations will continue during TMZ cycles up to a total of 10 vaccines unless progression occurs. Patients will be imaged bimonthly at the discretion of the treating oncologist without receiving any other prescribed anti-tumor therapy. Patients will undergo an additional leukapheresis for generation of DCs if needed to continue vaccinations. As part of standard care for these patients, upon tumor progression, participants may undergo stereotactic biopsy or resection. As this is not a research procedure consent will be obtained separately. However, if tissue is obtained, it will be used to confirm

tumor progression histologically and to assess immunologic cell infiltration and pp65 antigen escape at the tumor site.

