9.1.1 Randomization of Vaccine Site Pre-Conditioning Strategies

A randomization will be performed to assign patients to one of the three treatment strategies after completion of radiation with concurrent temozolomide. A permuted block randomization scheme stratified by *CMV* serology will be used to assign patients to treatment groups: unpulsed DCs pre-conditioning prior to vaccination #4, Td pre-conditioning prior to vaccination #4, or basiliximab infusions at vaccination #1 and #2 and Td pre-conditioning prior to vaccination #4.

As previously noted, the randomization of subjects to Group III has been terminated as of AMD 49. With this amendment, the randomization scheme stratified by *CMV* serology has been modified to assign patients to one of two treatment groups.

The administration of pre-conditioning agent (Td or unpulsed DCs) will be blinded for Groups I and II, however, the administration of the pre-conditioning agent (Td) and basiliximab for Group III will not be. Hence, patients and providers will know when a patient has been assigned to the third treatment group (please see randomization and blinding SOP 18.2 in appendices).

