9.4 Definition of Evaluable Subjects, On Study, and End of Study

Subjects evaluable for the analysis of the primary endpoints of DC migration will include all randomized patients in Groups I and II who receive the 4th DC vaccine. Survival analyses will include all randomized patients.

Once the patient signs an ICF, that subject will be considered “on study”. Rationale for taking patient off protocol treatment will be documented.

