15.1 Study Design Overview

This randomized phase II study will assess the impact of tetanus pre-conditioning on migration among newly diagnosed GBM patients who have undergone definitive resection and completed standard temozolomide and radiation treatment, as well as the impact of tetanus pre-conditioning and basiliximab together on survival. After completing standard of care radiotherapy with concurrent temozolomide, patients will be randomized to 1 of 3 treatment arms:

- Group I will receive DC vaccinations with *unpulsed DC pre-conditioning* prior to the 4th vaccination;
- Group II will receive DC vaccinations with *Td toxoid pre-conditioning* prior to the 4th vaccination; and
- Group III will receive *basiliximab infusions* prior to the 1st and 2nd DC vaccinations along with Td toxoid pre-conditioning prior to the 4th vaccination.

A permuted block randomization algorithm using a 1:1:1 allocation ratio will be used to assign patients to a treatment arm. Randomization will be stratified by CMV status (positive, negative), with the assignment to arms I and II being double-blinded (See Sections 9.1.1 and 9.1.7 for further details).

The study was initially activated with Groups I and II. However, approximately 2 months the study's initial activation, the study has been amended to include Group III.

Once accrual to Groups I and II are complete, a decision will be made concerning the accrual of additional patients to the Groups I and II in order to assess the impact of Td toxoid pre-conditioning within subgroups defined by CMV status. Options include continued accrual to both strata, accrual to only one stratum, or termination of accrual. Details are provided in Section 15.8.

Per Section 9.1, the study has been amended to terminate randomization to Group III. Rationale is provided in Section 9.1. Though randomization to Group III has been terminated, the analyses proposed for Group III will still be done even though the power of planned analyses will be greatly reduced due to a sample size smaller than anticipated within Group III.

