The study was closed to enrollment in April 2018 (Amendment 73). At the time the study was closed to new enrollment, a sufficient number of subjects have been enrolled to power the migration endpoint described in Section 15.9.3. An interim analysis of survival was initially planned after 35 patients were randomized to each Arm A and Arm B (Section 15.8). Survival analyses will still be conducted, but they may not be powered for the comparisons of survival described in Section 15.9.2. Exploratory immune analyses described in Section 15.7 will be conducted as planned.

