15.2 Analysis Sets

Subject to the availability of data, all randomized patients will be included in all analyses of correlative and efficacy endpoints.

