15.5.1 Key Primary Objective: Overall Survival

The Kaplan-Meier estimator will be used to describe the survival within each of the 3 treatment arms. Median survival will be estimated within each arm, with 95% confidence intervals. OS will be defined as the time between randomization and death, or last follow-up if alive. Two pairwise one-tailed log-rank tests will be conducted to assess the impact of Td and/or basiliximab. One test will compare the survival experience of patients in the TD toxoid arm (Group II) and the unpulsed DC arm (Group I), and the other test will compare the survival experience within the basiliximab arm (Group III) and the unpulsed DC arm (Group I). An intent-to-treat philosophy will be followed in these analyses.

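### The Group III v Group I survival and PFS tests, as written, use all Group I patients, including those randomised when Group III was not open

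*Combined protocol and SAP*

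**What the plan says.** Section 15.5.1 places two one-tailed pairwise log-rank tests under the key primary objective. The first compares Group II with Group I; "the other test will compare the survival experience within the basiliximab arm (Group III) and the unpulsed DC arm (Group I". Section 15.6.1 repeats both pairs for PFS, and 15.9.2 sets the survival tests at the one-sided 0.15 level. None of these sections limits the comparison by date of randomisation or stratifies it.

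The analysis sets are equally open. Section 9.4: "Survival analyses will include all randomized patients". Section 15.2, subject to data being available: "all randomized patients will be included in all analyses of correlative and efficacy endpoints".

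The arms were not open over the same period. Section 15.1 says that the study began with Groups I and II and that Group III was added about two months later. Section 9.1: "As of March 2017 (AMD 49), randomization of patients to Group III has been terminated"; its revised total of about 79 is given as "including 9 patients previously randomized to Group III". Section 9.1.1 adds that the randomisation scheme "has been modified to assign patients to one of two treatment groups". Enrolment closed in April 2018, about 13 months after Group III closed.

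Section 15.1 keeps the Group III comparisons: "the analyses proposed for Group III will still be done even though the power of planned analyses will be greatly reduced". Reduced power is the only consequence it names.

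**The concern.** A patient randomised to Group I after March 2017 could not have been assigned to Group III. The same holds for any patient randomised before Group III opened. For these patients the contrast with Group III is a comparison across periods, not a randomised one. If case mix, treatment delivery or later therapy changed between periods, the pooled test mixes that change with the effect of basiliximab plus Td, and the stated 0.15 level need not hold, in either direction. The comparison sits under the key primary objective and would be read as randomised. Low power, which the plan acknowledges, is a different problem.

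**Working it through.** **1. The plan's own figure.** Section 15.9.2 asks for 45 deaths per comparison (hazard ratio 0.5, one-sided 0.15, 90% power, equal arms). Schoenfeld: d = (z₀.₈₅ + z₀.₉₀)² / [0.25 × (ln 0.5)²] = (1.0364 + 1.2816)² / (0.25 × 0.4805) = 5.373 / 0.1201 = 44.7, so 45. It reproduces. Planned accrual does too: 2 × 1.75 + 27 × 1.17 = 35.1 per arm for Groups I and II, and 27 × 1.17 = 31.6 for Group III (stated as about 35 and 32).

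**2. What is left for Group III v Group I.** Group III has 9 patients. Even with 35 in Group I the two arms hold 9 + 35 = 44 patients, so 45 deaths cannot be reached.

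**3. How many controls are concurrent.** The documents do not say. Under the 1:1:1 allocation in 15.1, about 9 Group I patients would be expected alongside 9 in Group III. The final Group I size is not given either. Section 15.1 says that "a sufficient number of subjects have been enrolled to power the migration endpoint", which under 15.5.2 means 12 per arm receiving vaccine 4; the goal in 15.9 is 35. So about 12 to 35 fits the text. The non-concurrent share is then (12 − 9)/12 = 25% to (35 − 9)/35 = 74%. The part from before Group III opened would be 2 × 1.75 = 3.5 patients at the planned rate. It may be near zero, because randomisation follows about 6 weeks of radiotherapy and 15.9 says its timing estimates no longer hold.

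**4. What drift would do, if there were any.** Assumptions: exponential survival, median 12 months, censoring at 36 months, no effect of Group III against concurrent controls, 9 v 9 concurrent patients, one-sided 0.15 log-rank test, 40,000 simulated trials per scenario. The hazard ratio in the first column (non-concurrent to concurrent Group I) is assumed, not estimated. Entries are the error rate against all Group I patients.

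| Assumed ratio | Group I = 12 | 20 | 35 |
|---|---|---|---|
| 0.67 | 0.105 | 0.055 | 0.032 |
| 0.8 | 0.126 | 0.085 | 0.065 |
| 1 (no drift) | 0.150 | 0.140 | 0.135 |
| 1.25 | 0.180 | 0.214 | 0.248 |
| 1.5 | 0.196 | 0.279 | 0.362 |

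With concurrent controls only, the rate is 0.155–0.162 throughout. If 4 of 35 Group I patients came before opening and only post-closure patients drift, the range is 0.039 (ratio 0.67) to 0.319 (ratio 1.5). A separate simulation with staggered entry and the same 4 unshifted patients (6,000 runs) gave 0.05 to 0.28.

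**5. Estimation.** At Group I = 35 with a true log hazard ratio of 0, the pooled estimate averages −0.27 at ratio 1.5 and +0.33 at 0.67, that is, hazard ratios of about e^−0.27 = 0.76 and e^0.33 = 1.39. Coverage of the 95% interval is 0.911 and 0.861, against 0.944–0.951 for concurrent-only. The root-mean-square error favours pooling: 0.42–0.55 over Group I sizes 12, 20 and 35, against 0.56–0.58.

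**6. Stratifying by period.** In a period with no Group III patients, the observed-minus-expected term and its variance are both zero. A log-rank test stratified by randomisation period is therefore the concurrent-only test.

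**The case against.** **Little turns on this test.** Group III has 9 of about 32 planned patients and was stopped because of another study's results. Section 15.1 concedes low power for this arm and says survival analyses generally may not be powered. Nine patients cannot support a phase III decision. This stands, and it sets the severity.

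**Drift is not shown.** A reader might infer from 15.9 that the trial's conduct or prognosis changed over time. The text does not support that. It says the rate of randomisation varied, because of the number of arms and early vaccine contamination, as the reason for not re-estimating timelines. It says nothing about outcome, and problems called early do not show that patients randomised after March 2017 differed. What remains is that the concurrent comparison needs no assumption of stable prognosis, while the pooled one does.

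**Pooling estimates more precisely.** The root-mean-square error is lower with all Group I patients, so for a descriptive result the choice of main analysis is partly a judgement. This too stands and is the reason for showing both. The case for concurrent-only as the main result is that it remains a randomised comparison and its interval keeps its coverage.

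**Intention-to-treat requires everyone.** It requires analysis as assigned. Limiting the comparison to patients who could have been assigned to either arm keeps that.

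**Conclusion.** The omission is clear from the text: no section restricts the Group III v Group I OS and PFS tests to the shared randomisation period or stratifies by it, and 9.4 and 15.2 bring in all of Group I. Whether any bias follows is unknown.

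Two stronger readings are not supported. One is that the comparison is biased: the documents show no drift and give neither its size nor its direction. The other is that the error rate is 0.36: that figure needs 35 patients in Group I, in a study closed early, and a 1.5-fold hazard in every non-concurrent control. At 12 patients the whole range is 0.11–0.20. All these figures rest on the inferred 9 concurrent controls and the assumed drift.

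Group II v Group I is not affected in this way, since those arms were randomised side by side throughout. Severity: minor. Confidence is high about the missing specification only.

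**What to change.** In 15.5.1 and 15.6.1, make the main Group III comparison one against Group I patients randomised while Group III was open; a log-rank test stratified by randomisation period is equivalent. Add this exception to 9.4 and 15.2, which would otherwise contradict it. Report the number of concurrent controls. Label the comparison descriptive, with Kaplan–Meier curves and a hazard ratio with its 95% confidence interval. Show the comparison with all Group I patients alongside as a sensitivity analysis.

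The change is to wording only. The price is wider intervals, a larger root-mean-square error (about 0.57 against 0.42–0.55) and some power: about 0.60 at a hazard ratio of 0.5 without drift, against 0.63–0.70 for Group I totals of 12 to 35, in an arm already stopped.

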15.5.2 Other Primary Objective: Migration

Within Groups 1 and 2, the percentage of ¹¹¹In-labeled DCs reaching inguinal nodes at vaccination #4 is calculated from the initial signal at the injection site in the groin to 48 hours post-vaccination. A Wilcoxon rank-sum test will be used to compare assigned treatment groups (Groups I and II) with respect to migration. This analysis will be based upon the first 12 patients within each arm (Groups I and II) that receive vaccination #4.

15.5.3 Other Primary Objective: Survival Among *CMV* Positive Patients

To assess the impact of Td pre-conditioning on survival among patients who are *CMV* positive, an analysis similar to those described for the key primary objective will be generated within the subgroup of patients who are *CMV* positive. Specifically, the Kaplan-Meier estimator will be used to describe the survival among *CMV* positive patients within Groups I and II. Median survival will be estimated within each of these 2 treatment arms, with 95% confidence intervals.

OS will be defined as the time between randomization and death, or last follow-up if alive. A log-rank test will be conducted to assess the impact of pre-conditioning. An intent-to-treat philosophy will be followed in these analyses.

Subgroup analyses will be underpowered and descriptive unless a decision is made to continue accrual and treatment of CMV positive patients after the completion of accrual to Group III (See Section 15.8).

15.5.4 Other Primary Objective: Survival Among CMV Negative Patients

Analyses similar to those described in section 15.5.3 for patients who are CMV positive will be conducted among patients who are CMV negative.

15.6 Secondary Objectives

Secondary objectives and endpoints that are presented in section 8 include an examination of the impact of Td pre-conditioning with and without basiliximab on progression-free survival, as well as the impact of Td pre-conditioning on progress-free survival within patient subgroups defined by CMV status.

15.6.1 Key Secondary Objective: PFS

The Kaplan-Meier estimator will be used to describe progression-free survival (PFS) within each arm. Median PFS will be estimated within each of the 3 treatment arms, with 95% confidence intervals. PFS will be defined as the time between randomization and initial failure (disease progression or death). If the patient remains alive without disease progression, PFS will be censored at the time of last follow-up. Two pairwise log-rank tests will be conducted to assess the impact of Td and/or basiliximab. One test will compare the PFS experience of patients in the TD toxoid arm (Group II) and the unpulsed DC arm (Group I), and the other test will compare the survival experience within the basiliximab arm (Group III) and the unpulsed DC arm (Group I). An intent-to-treat philosophy will be followed in these analyses.

15.6.2 Other Secondary Objective: PFS Among CMV Positive Patients

To assess the impact of Td pre-conditioning on PFS among patients who are CMV positive, analysis similar to those described for the key primary objective will be generated within the subgroup of patients who are CMV positive. Methods similar to those described in Section 15.5.3 will be used.

15.6.3 Other Secondary Objective: PFS Among CMV Negative Patients

Analyses similar to those described in section 15.6.2 for patients who are CMV positive will be conducted among patients who are CMV negative.

15.7 Exploratory Objectives

Changes from baseline in immune response as measured by ELISpot will be explored at each follow-up assessment and within each treatment group. Though analyses are exploratory, a Kruskal-Wallis will be used to compare treatment groups relative to maximum changes in ELISpot observed. A similar analysis will be conducted for levels of T_{Reg}, CCL3, and other

inflammatory soluble factors. Parametric analyses, such as an analysis of variance, may be used in lieu of a Wilcoxon test if underlying assumptions are satisfied.

When ELISpot results are positive, the extent of T cell functionality will be assessed. For each patient, the proportion of patients with 1, 2, and 3 functions will be determined. A negative ELISpot will be assumed to have 0 functions. Within each treatment group, changes from baseline in the percentage of patients with 0, 1, 2 and 3 functions will be explored Hotelling's T-test or a nonparametric equivalent. Additional statistical analyses may be conducted to changes in polyfunctionality, as well as to address other exploratory goals

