12.7.5 Immunologic Assessments

Immunological response evaluations for baseline values will be conducted on the leukapheresis sample used to generate the DCs and on a second leukapheresis sample obtained 4 ± 2 weeks after the third immunization. Blood work for immunologic monitoring (9 yellow and 2 red top tubes) will be drawn before basiliximab (Group III only), vaccine #1, and then as described above after vaccine #3 and/or at progression (whichever comes first). For subjects who complete all 10 study vaccines without progressing, an attempt will be made to obtain blood for immunologic monitoring 2-3 times a year at standard Duke neuro-oncology visits and at progression (whichever comes first). The total amount of blood required for this purpose will be about 90 mLs. The immune monitoring blood drawn at vaccine #1 will be analyzed for baseline CCL3 level. Plasma from the yellow top tubes will be collected at each time point listed where immunologic monitoring is done. Blood work for sub-clinical autoimmunity will be drawn before basiliximab (Group III only), or vaccine #1 (all other groups), and repeated only if clinically indicated. Laboratory evaluations to detect subclinical disease will be obtained as follows: serum thyroglobulin Ab (Lab Code 1802105), rheumatoid factor (Lab Code 5560195), antinuclear Ab (Lab Code 5560214), Thyroid Profile (Lab Code 1850277), and CMP (Lab Code 1004261). A comparison of pre-therapy lymphocyte functions to those at intervals after each immunization will be made. These tests may provide evidence for the development of immune responses following DCs immunization and will play an important role in the design of future DC-based clinical trials. Cellular immune responses to pp65 will be measured in a tiered approach. First, PBMCs will be assessed at pre-treatment (leukapheresis) and during treatment for responses to pp65 using a qualified IFN- γ ELISpot. If positive in the ELISPOT assay, pp65 antigen-specific T cell response will be measured by polyfunctional T cell assays using 8-9 color panels previously optimized in our laboratory which includes detection of CCL3 on T cells. The effect of treatment on cytokines and other soluble factors will be assayed in the serum/plasma. Serum/plasma will be measured to determine levels of CCL3 from the blood drawn at the vaccine #1 visit (in ALL Groups), and repeated at the SPECT/CT imaging visits (2 yellow and 1 red top tubes, in Groups I and II only). T_{Reg} kinetics will be measured by using a constellation of markers specific for T_{Regs} such as foxp3, CD25 and CD4.

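### The one between-group immune test named in Section 15.7 is an omnibus test that appears to include the nine basiliximab patients, so a significant ELISpot or TReg result cannot be read as a Td effect

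*Combined protocol and SAP*

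**What the plan says.** Section 15.7 names one test between groups: "a Kruskal-Wallis will be used to compare treatment groups relative to maximum changes in ELISpot observed". It then adds: "A similar analysis will be conducted for levels of" TReg, CCL3 and other inflammatory soluble factors. It names no pairwise contrast, post-hoc test, alpha level or covariate. The polyfunctionality analysis is not between groups: "Within each treatment group, changes from baseline in the percentage of patients with 0, 1, 2 and 3 functions will be explored".

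Two sentences leave room for other analyses. One is "Parametric analyses, such as an analysis of variance, may be used in lieu of a Wilcoxon test if underlying assumptions are satisfied", although Section 15.7 specifies no Wilcoxon test. The other is "Additional statistical analyses may be conducted to changes in polyfunctionality, as well as to address other exploratory goals".

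Section 15.7 does not say how many groups enter the Kruskal-Wallis test. Three statements elsewhere imply three:
- Section 15.2 puts every randomized patient into the correlative analyses, subject to available data.
- Section 15.1 keeps the Group III analyses and concedes their low power.
- Section 15.1 also says that the Section 15.7 analyses proceed unchanged after enrollment closed.

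Section 9.1 gives the projected total as about 79, "including 9 patients previously randomized to Group III". On the study that served as the model for Group III, it says: "Recent analyses of REGULATE data have shown that although the regulatory T cells were depleted, the cells did not show pp65 reactivity".

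**The concern.** ELISpot measures the response to pp65, and TReg level is another of the tested markers. Both are variables on which the related study gives reason to expect Group III to differ. An omnibus test that includes Group III can therefore be significant when Groups I and II are identical, and the p-value does not show which arm is responsible.

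The plan handles its other endpoints differently. Sections 15.5.1 and 15.6.1 specify II versus I and III versus I for OS and PFS, and Section 15.5.2 specifies a two-group Wilcoxon test for migration. Only the immune section lacks a direct Td contrast. Section 15.1 says that the survival comparisons may not be powered after closure, so readers may lean more on the immune results.

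The second issue is precision. The outcome is a change from baseline, but neither the baseline value nor CMV serostatus enters as a covariate. Randomization is stratified by CMV serology, about half the patients are expected to be positive (Section 15.9.4), and the ELISpot antigen is a CMV protein.

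**Working it through.** **Inputs from the documents.** The target is 35 patients in each of Groups I and II (Section 15.9), with 9 in Group III (Section 9.1). 35 + 35 + 9 = 79 reproduces the stated total. The documents give no power, alpha or sample size for the immune test, so there is no such figure to reproduce.

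**Assumptions.** Alpha is 0.05 two-sided. The changes are normal with SD 1. The Group III shift is varied because the documents give no size for it.

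**Tests compared.**
- The three-group Kruskal-Wallis statistic is H = 12/[N(N+1)] × Σ(R_j²/n_j) − 3(N+1), where R_j is the rank sum of group j and N = 79. It is referred to chi-square with 2 df.
- The II versus I rank test uses the same formula on those two groups (N = 70, 1 df), which is equivalent to a Wilcoxon test.

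**Rejection with no Td effect (20,000 simulated trials per row, 35/35/9).**

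| Group III shift (SD) | Kruskal-Wallis | II v I | Kruskal-Wallis significant, II v I not |
|---|---|---|---|
| 0 | 5% | 5% | 2% |
| 0.25 | 8% | 5% | 5% |
| 0.5 | 20% | 5% | 16% |
| 0.75 | 40% | 5% | 36% |
| 1.0 | 65% | 5% | 60% |
| 1.5 | 95% | 5% | 90% |

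With fewer evaluable patients, rejection at a 1 SD shift is 51% (25/25/7) or 53% (12/12/9).

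**Power when Td does have an effect (35/35/9).**

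| Td effect (SD) | Group III effect (SD) | Kruskal-Wallis | II v I | Loss (points) |
|---|---|---|---|---|
| 0.5 | 0.5 | 45% | 51% | 6 |
| 0.7 | 0 | 75% | 80% | 5 |
| 0.7 | 0.35 | 70% | 81% | 11 |
| 0.7 | 0.7 | 76% | 80% | 4 |
| 0.75 | 0.75 | 82% | 86% | 4 |

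The loss is therefore about 4 to 11 points when Group III lies at or between the other two groups.

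**Baseline covariate.** Take one follow-up, equal variances of 1 and a baseline to follow-up correlation ρ, which is assumed. The variance of a change score is 2(1−ρ). After adjustment for baseline it is 1−ρ². The ratio is (1−ρ²)/[2(1−ρ)] = (1+ρ)/2, which is 0.65, 0.75 and 0.85 for ρ = 0.3, 0.5 and 0.7. For a difference of 0.75 SD with 35 per group, power by the normal approximation rises from 76% to 91%, from 88% to 95%, and from 98% to 99%.

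The planned outcome is a maximum over visits, tested on ranks, so this formula is only a guide. Simulating the maximum change over repeated visits at ρ = 0.5 gave 66% power for the unadjusted rank test and 82% for rank ANCOVA. A repeat with five visits and a Td shift of 0.5 SD gave 68% and 83%. Visit number, correlation and effect size are all assumed. The gain from adding CMV serostatus is not quantified, because the documents give no ELISpot values by serostatus.

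**The case against.** The strongest reply is that these endpoints are descriptive. Table 1 sets out to describe or measure the immune markers and does not ask for a Td effect on them. Section 15.7 also has changes explored within each group at each assessment, so arm summaries would accompany the p-value and show which arm drives it. TReg monitoring is tied to the basiliximab rationale (Section 7.3), and keeping Group III is a disclosed choice. Unspecified further analyses are allowed, so a pairwise test is not excluded. All of this stands and limits the severity. It does not supply a prespecified Td contrast.

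A reader might infer several stronger points that the documents do not support:
- **Inflated false-positive rate.** If basiliximab shifts a marker, the groups do differ and the omnibus rejection is correct. The 65% and the 5% above refer to different null hypotheses.
- **Baseline ignored.** The outcome already subtracts baseline. Only the covariate is missing, and stratified randomization guards against CMV imbalance.
- **CCL3 test impossible.** Section 12.7.5 takes CCL3 at vaccine #1 in all groups "and repeated at the SPECT/CT imaging visits (2 yellow and 1 red top tubes, in Groups I and II only". But Section 15.2 works with the data available, and on two groups the Kruskal-Wallis is the two-group rank test. Table 4 (note 6) also collects plasma at the other monitoring visits, and Section 12.7.5 allows multiplex CCL3 assays without limiting them to certain groups.
- **Group III closed because TRegs were depleted.** Section 9.1 concedes the depletion; the unfavorable findings are the absent pp65 reactivity and reduced activation.

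**Conclusion.** The concern holds as a gap in specification. The named between-group immune test does not isolate Td, and for ELISpot and TReg the protocol itself gives reason to expect Group III to differ. The size depends on an unknown shift: it is minor at 0.25 SD (8% rejection) and serious from about 0.75 SD (40%) upward. The power loss for Td is modest, and the missing covariates cost precision without causing bias.

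The conclusion rests on reading Sections 15.1 and 15.2 as placing Group III in the test, on group sizes of 35/35/9 (35 is a target, and the numbers reached are not stated), on an alpha of 0.05, and on normal changes. Because the endpoints are exploratory, no primary or secondary conclusion depends on this test.

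**What to change.** In Section 15.7:
- Name Group II versus Group I as the Td comparison for each marker. Analyze the planned change measure by rank ANCOVA, or by ANCOVA on log counts, with the baseline value and CMV serostatus (the randomization stratum) as covariates.
- Report Group III separately, either descriptively or, for TReg, as a secondary III versus I contrast.
- Base each CCL3 comparison on time points measured in both groups being compared.
- Remove or define the reference to a Wilcoxon test, and state the alpha level or say that p-values are descriptive.

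The cost is a paragraph of SAP text and a few lines of code, with no new data. The single omnibus p-value across arms is lost as the headline test.
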